3.4. The PK Analysis Set

The PK analysis set includes all randomized patients who received any study drug and have at least 1 qualified (non-missing) blood sample following the first administration of study drug; it is based on the treatment received (as treated).

3.5. The Anti-Drug Antibody Analysis Set

The anti-drug (fasinumab) antibody (ADA) analysis will include all randomized and treated patients who have at least 1 post-dose ADA result after the first dose of study treatment.

4. ANALYSIS VARIABLES

4.1. Demographic and Baseline Characteristics

Baseline characteristics will include standard demography (e.g., age, gender, race, ethnicity, weight, height, etc.), disease characteristics including baseline LBPI NRS score, duration of chronic back pain, maximum K-L score at any knee or hip joint at screening, use of paracetamol/acetaminophen as rescue medication during the pre-randomization period, medical history, and medication history for each patient.

The following demographic and baseline characteristic variables will be summarized by treatment group based on data collected in the eCRF:

- Age at screening (years)
- Age category based on tertiles.
- Age category (<65, ≥65 years)
- Sex (Male, Female)
- Race (American Indian/Alaskan Native, Asian, Black/African American, Native Hawaiian/Other Pacific Islander, White and Other)
- Ethnicity (Hispanic/Latino: Yes or No)
- Baseline Weight(kg)
- Baseline Height(cm)
- Baseline Body mass index (BMI) calculated from weight and height
- Baseline LBPI NRS score
- Baseline LBPI NRS score strata (< 7, ≥ 7)
- Duration of chronic back pain (years)
- Duration of chronic back pain strata (< 5 years, ≥ 5 years)
- Maximum Kellgren-Lawrence score at any knee or hip joint at screening
- Maximum Kellgren-Lawrence score at any knee or hip joint at screening (≤2, >2)
- Use of rescue medication during pre-treatment period (Paracetamol/Acetaminophen: Yes or No)

Additional baseline characteristics will be summarized if needed.

4.2. Medical History

Patient medical history will be dictionary coded by Preferred Term (PT) and associated Primary System Organ Class (SOC) according to the MedDRA version 18.0.

4.3. Pre-Treatment / Concomitant Medication

Medications and procedures will be recorded from the day of informed consent until the EOS visit. Medications will be coded to the ATC level 2 (therapeutic main group) and ATC level 4 (chemical/therapeutic subgroup), according to the WHO Drug Dictionary (WHODD) March 2015 version. Prior medications are defined as medications starting prior to the first

administration of study drug. Prior procedures are defined as procedures performed prior to the first administration of study drug.

Concomitant medications are defined as medications starting prior to *or* during the on-treatment period (as defined in [section 4.5](#)) and ending during or after the on-treatment period.

Post treatment medications are medications starting after the on-treatment period.

Prohibited medications include medications containing NSAIDS (oral or topical; except up to 100mg/day of aspirin for cardiac prophylaxis) and opioid analgesic medications (including tramadol). Opioid analgesic medications (including tramadol) are prohibited through the week 16 study visit. Patients will be directed not to take concomitant medications that contain NSAIDS (oral or topical, except up to 100mg/day of aspirin, which is permitted for cardiac prophylaxis) until at least 16 weeks after the last dose of study drug. Other excluded drugs include:

- Any other investigational agent
- Cyclosporine
- Azathioprine
- Medical marijuana
- Tumor necrosis factor antagonists
- Corticosteroids (topical and inhaled formulations are permitted)
- Tocilizumab
- Abatacept
- Cyclobenzaprine, carisoprodol, orphenadrine, tizanidine
- Muscle relaxants

Prohibited concomitant medications will be summarized separately by ATC class, preferred term and treatment group.

Patients will be counted once in all ATC categories linked to the medication.

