In clinical studies completed to date, fasinumab was generally well tolerated. Arthralgia, joint swelling, peripheral edema, hypoesthesia, and myalgia were more frequently reported in fasinumab patients compared with placebo patients. In neurological evaluations, abnormalities in vibration sense were more frequent in fasinumab patients compared with placebo patients. These adverse events (AEs) or physical examination abnormalities were mild to moderate in intensity and transient in nature (fasinumab Investigator's Brochure 2015). Data from tanezumab and fulranumab demonstrated an increased risk of arthropathy events. Adjudicated Arthropathy is an umbrella term for the following conditions: rapidly progressing OA, subchondral insufficiency fracture, or osteonecrosis (Roemer 2015). Analyses of the tanezumab data by its sponsor showed that the risk of arthropathy events increases with tanezumab dose and is further increased with the concomitant use of chronic NSAIDs (>90 days) (Lane 2010). Most cases occurred in patients with a documented history of OA. To date, 1 case of possible adjudicated arthropathy has been observed with fasinumab.

Based on the potential risk of adjudicated arthropathy events identified with tanezumab and fulranumab, the US Food and Drug Administration (FDA) placed the class of anti-NGF antibodies on clinical hold in 2010. Following review of anti-NGF antibody clinical data in March 2012, the FDA determined that clinical studies with anti-NGF therapies could resume if mitigation strategies are implemented to minimize the risk of adjudicated arthropathy. To address concerns about potential events of adjudicated arthropathy, a risk-mitigation approach is being implemented for all fasinumab studies, as outlined in Section 7.4.1.

In 2012, all sponsors were put on clinical hold after non-clinical studies of other anti-NGF monoclonal antibodies identified adverse changes in the sympathetic nervous system of mature animals of several species. After additional non-clinical data were provided to FDA, studies

with up to 16 weeks of exposure were allowed. Patients will be monitored for any signs or symptoms of potential sympathetic nervous system dysfunction.

Additional background information on the study drug and development program can be found in the Investigator's Brochure.

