5.7. Concomitant Therapy

Any treatment administered from screening until the end of study (week 36) is considered concomitant medication. This includes medications that were started prior to the study and are ongoing during the study.

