5.4. Prohibited Medications

Prohibited medications, dictionary coded by WHO, will be descriptively summarized by ATC class, preferred term and treatment group for patients in the SAF similar to the summary of concomitant medications.

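### The SAP's prohibited-medication table follows the on-treatment period, so NSAID courses (and, in some early stoppers, opioid courses) begun later but still under the ban are not identified as prohibited

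*SAP*

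**What the plan says.** SAP 4.3 lists the prohibited drugs and repeats the protocol's bans. For opioids it says: "Opioid analgesic medications (including tramadol) are prohibited through the week 16 study visit". NSAIDs, apart from low-dose aspirin for cardiac prophylaxis, are barred until at least 16 weeks after the last dose. Under Protocol 5.7.2 both bans start at the pre-randomization visit.

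The same SAP section sets the tabulation rule: "Prohibited concomitant medications will be summarized separately by ATC class, preferred term and treatment group". It defines concomitant medications as those starting before or during the on-treatment period and "ending during or after the on-treatment period". Anything later falls in another class: "Post treatment medications are medications starting after the on-treatment period". SAP 4.3 points to section 4.5 for the on-treatment period, but the definition is in 5.8: first dose to the later of 4 weeks after the last SC dose and 8 weeks after the last IV dose.

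SAP 5.4 describes the same summary without the word concomitant. It gives no period and says only that the table is "for patients in the SAF similar to the summary of concomitant medications". SAP 5.3 separately plans tables of prior, concomitant, post-treatment and on-study medications, the last being concomitant plus post-treatment.

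Protocol 5.7 uses the term more widely: "Any treatment administered from screening until the end of study (week 36) is considered concomitant medication".

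**The concern.** The SAP states the bans and then tabulates departures from them on a window that ends sooner. A reader of the prohibited-medication table would take it as the record of adherence to the bans, yet it omits NSAID courses that begin after the on-treatment period while the ban still applies.

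NSAID use bears on the trial's main safety question. Protocol 1.1 reports, from tanezumab data, that arthropathy risk rises with dose and further with chronic NSAID use of more than 90 days. SAP section 1 records that the trial was put on partial hold after an adjudicated arthropathy event, that dosing stopped early, and that patients are followed to week 36 partly for safety. The summaries of special-interest events and joint replacements (SAP 5.8.2 and 5.8.3) plan no link to NSAID use. As written, then, no planned table shows by arm how much NSAID use occurred within the banned window. The early stop of dosing also makes patients with few doses a real group, and in some of them the opioid ban outlasts the on-treatment period too.

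**Working it through.** **Inputs.** SC doses are due on day 1 and at weeks 4, 8 and 12 (days 1, 29, 57, 85); IV doses on day 1 and at week 8 (days 1, 57) (Protocol 5.1 and Table 1). The on-treatment rule is in SAP 5.8. The bans are in SAP 4.3 and Protocol 5.7.2. The week 16 visit is due on day 113.

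**Formulas.**
- On-treatment end = max(last SC day + 28, last IV day + 56)
- NSAID ban end = last dose day of either route + 112 (the stated minimum)
- Opioid ban end = day 113
- Gap = ban end − on-treatment end, or 0 if negative

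**Check against the plan's own figure.** Protocol 9.5.3.1 equates the end of the on-treatment period with week 16. For a full course, max(85 + 28, 57 + 56) = max(113, 113) = day 113, which is week 16. The figure reproduces.

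**Results, on-schedule dosing.**

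| Last SC / last IV | On-treatment ends | NSAID ban ends | NSAID gap | Opioid gap |
|---|---|---|---|---|
| Day 1 / day 1 | max(29, 57) = day 57 | 1 + 112 = day 113 | 56 days (8 weeks) | 56 days (8 weeks) |
| Week 4 / day 1 | max(57, 57) = day 57 | 29 + 112 = day 141 | 84 days (12 weeks) | 56 days (8 weeks) |
| Week 8 / day 1 (week 8 IV not given) | max(85, 57) = day 85 | 57 + 112 = day 169 | 84 days (12 weeks) | 28 days (4 weeks) |
| Week 8 / week 8 | max(85, 113) = day 113 | 57 + 112 = day 169 | 56 days (8 weeks) | 0 |
| Week 12 / day 1 (week 8 IV not given) | max(113, 57) = day 113 | 85 + 112 = day 197 | 84 days (12 weeks) | 0 |
| Week 12 / week 8 (full course) | max(113, 113) = day 113 | 85 + 112 = day 197 | 84 days (12 weeks) | 0 |

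The NSAID gap is 8 to 12 weeks in every pattern. After a full course it is days 114 to 197, or 12 of the 28 weeks from first dose to the end of the ban (12/28 = 43%). That percentage is a share of calendar time, not of missed use.

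The opioid gap is above zero only in the first three rows: no week 8 IV dose, and last SC dose at week 8 or earlier.

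**Where the gap use goes.** A course first started in the gap is post-treatment under SAP 4.3, so it enters the post-treatment and on-study tables of SAP 5.3 without a prohibited label. For a full-course patient the post-treatment table runs from week 16 to week 36. It therefore mixes NSAID use under the ban (weeks 16 to 28) with use after the ban (weeks 28 to 36).

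**Before the first dose.** Use after the pre-randomization visit that stopped before dosing is a prior medication only, so it is also outside a table limited to concomitant drugs.

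**The case against.** A reader might infer that banned NSAID use after treatment goes uncounted or unmonitored. The documents do not support that. Medications are recorded to the end-of-study visit, and an NSAID started at week 18 appears in two planned tables. What is missing is its identification as prohibited.

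Nor is all use during the gap affected. A course begun before or during the on-treatment period and continued past it still meets the concomitant definition and is already in the prohibited table. Only courses first started in the gap are at issue, and the documents give no count of these.

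A second tempting inference is that the table misses the very exposure Protocol 1.1 names as raising arthropathy risk. That exposure is chronic use of more than 90 days. A course confined to the gap lasts at most 84 days, so it cannot reach that length without continuing past the end of the ban. Chronic use begun on treatment is already captured.

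Third, the text can be read more kindly. SAP 4.3 writes the ban windows into its own description and, in the NSAID sentence, uses concomitant for a period longer than the on-treatment period. SAP 5.4 drops the word. One could argue that each class is meant to be summarized over its own ban. But the tabulation sentence uses a term defined in the same section, and 5.4 is modeled on the concomitant summary. If 5.4 were read as covering all periods, it would label opioid use after week 16, and NSAID use after the ban ends, as prohibited. The ambiguity is real and 5.4 does not settle it.

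Finally, the efficacy consequence is slight. The primary analysis stops at 5 weeks after the last dose: day 36 after a day 1 dose only (1 + 35), and day 64 after a last dose at week 4 (29 + 35). Most of the opioid gap in those patients, days 58 to 113, lies beyond it. The FAS sensitivity analysis reaches week 16, but no efficacy model takes the prohibited-medication table as input.

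**Conclusion.** The mismatch stands, as a limited defect in a descriptive safety table. Followed as written, SAP 4.3 does not identify as prohibited any NSAID course first started after the on-treatment period but within 16 weeks of the last dose: a gap of 8 to 12 weeks, and 12 weeks for a full-course patient. The same holds for opioid courses over 4 to 8 weeks, in the narrow group set out above. It is not a general feature of early stopping, because a patient who received the week 8 IV dose has no opioid gap.

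The use is recorded and tabulated elsewhere without a flag, and no efficacy estimate changes. The dates assume on-schedule doses and visits; the 7-day windows allowed for each would shift them by days. How many courses fall in the gap cannot be known from the documents.

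**What to change.** In SAP 4.3 and 5.4, flag and summarize prohibited use by the ban window the documents already state for each class, across prior, concomitant and post-treatment medications:

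- **Opioids:** from the pre-randomization visit through the week 16 visit.
- **NSAIDs, except permitted low-dose aspirin:** from the pre-randomization visit to 16 weeks after the patient's own last dose.

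The documents state no end date for the other excluded drugs, so the SAP should say what period the table uses for them. Correct the cross-reference for the on-treatment period from 4.5 to 5.8. Optionally, list NSAID use for each adjudicated arthropathy and each joint replacement; neither document promises this.

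The cost is SAP wording and a small date derivation on data already collected to week 36. The flag will depend on the partial-date rules in SAP 6.3. For example, a start date known only to the year of first dose is set to the first dose date, so some gap courses may be misplaced. No clinical rule and no efficacy analysis changes.

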4.4. Efficacy Variable

4.4.1. Primary Efficacy Variable

The primary endpoint in the study is the change from baseline to week 16 in the average daily Low Back Pain Intensity (LBPI) score on an 11-point (0-10) Numerical Rating Scale (NRS).

Baseline average daily LBPI NRS score is defined as the average of the non-missing daily LBPI NRS scores for 5 days prior to randomization (from Day -4 to Day 1). Average daily LBPI NRS scores is defined as the average of the non-missing daily LBPI NRS scores for the 7 days before and including nominal visit. The daily NRS score for the week 16 nominal visit day is missing for all patients due to operational difficulties which resulted in the daily entry not being captured on the clinical visit day since diaries are available starting at 6pm and clinical visits typically happen during the day with diaries being returned at the end of the visit. Therefore the average at week 16 will be based on 6 days.

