5. Patients will be trained on using the EDiary after initial patient eligibility has been confirmed during the screening period. Patients will use the EDiary to report their daily NRS LBP score and daily use of paracetamol/acetaminophen through the week 16 visit.
6. Study drug administration will be the last procedure at each dosing visit, and will be done after all laboratory samples have been collected and all study assessments and procedures are performed including blood draws for drug concentration and ADA. At the day 1 and week 8 visits, patients will receive the SC injection first, followed by the IV infusion. After IV administration of study drug, patients will be observed in the clinic for approximately 2 hours for evidence of a hypersensitivity reaction, and for 1 hour after SC dosing.

7. At the screening and pre-randomization visits, study staff will review the “Reporting Your Pain” brochure with the patient to ensure the patient understands how to report pain accurately. At subsequent clinic visits patients will be asked to review the “Reporting Your Pain” brochure themselves. At the screening visit, study staff will also review with the patient the “Participating in a Research Study: What You Need to Know” brochure.
8. Low back pain intensity NRS score will be recorded by the site at the screening visit and at the pre-randomization visit, and by the patient each day (at approximately 6:00 PM) using the EDiary, starting during the pre-randomization period through week 16.
9. If the pulse is less than 45 bpm at any visit after the randomization visit, an ECG with rhythm strip will be obtained and sent to the central reader to confirm the heart rate and rhythm.
10. The physical examination should include an exam of the knee, hip, and shoulder joints.
11. Imaging (X-ray and/or MRI) will be considered for worsening joint pain, despite treatment with analgesics, which is inconsistent with the normal progression of OA and lasts for at least 2 weeks (or less, at the discretion of the investigator).
12. In the event that a patient must undergo TJR surgery during the study, the patient will complete the early termination visit and the procedures outlined in the schedule of events for TJR follow-up (Table 3). The early termination visit should be completed before TJR surgery if at all possible. TJR questionnaires are Knee Society Score questionnaire for knee replacements or Harris Hip Score questionnaire for hip replacements.

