6.2.4. Baseline/Randomization Visit (Day 1)

If a patient has met all screening eligibility criteria, study sites will complete the procedures as detailed in the schedule of events for the baseline visit. The patient reported outcomes assessments at this and subsequent visits should be completed prior to all other assessments. All laboratory samples at this and subsequent visits must be collected and all study procedures must be performed before study drug is administered. At dosing study visits, urine pregnancy testing will be done and read before the study drug is administered. In the event of a positive urine pregnancy test result, the patient should have a serum pregnancy test with a negative result in order to continue study participation. If the serum pregnancy test is positive, the patient should be withdrawn from study drug and should be asked to return to the clinic for all remaining study visits per the visit schedule (see [Section 6.2.7](#)).

The date of the first dose of study drug is designated as day 1. All subsequent visits should be scheduled based on this date.

6.2.5. Weeks 1 through 16

Complete visits and assessments are outlined in the schedule of events ([Table 1](#)). The patient reported outcomes should be completed prior to all other assessments. All study procedures should be completed before administration of study drug. The last dose of study drug is administered at week 12. Patients who discontinue study drug should return for the remaining study visits, if possible. If patients are not able to continue study participation, they should return for an early termination visit, at which the treatment-period early termination visit assessments will be performed per the schedule of events.

At dosing study visits, urine pregnancy testing will be done and read before the study drug is administered. Study drug will be withheld in the event of a positive urine pregnancy test result. In the event of a positive urine pregnancy test result, a serum pregnancy test must be performed. If the serum pregnancy test is negative, the patient may continue study participation. If the serum pregnancy test is positive, the patient must be permanently discontinued from study drug and should be asked to return to the clinic for all remaining study visits per the visit schedule ([Section 6.2.7](#)).

6.2.6. Weeks 20 through 36

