9.6. Additional Statistical Data Handling Conventions

The following analysis and data conventions will be followed:

Definition of baseline:

- Baseline will be defined as the average daily LBPI score for the 5 days before randomization. If any of the 5 baseline scores are missing, the baseline value will be calculated over the remaining observations. Similarly, the week 16 value will be defined as the average daily LBPI score for the 7 days before and including day 113 (week 16). If any of the 7 week 16 scores are missing, the week 16 value will be calculated over the remaining observations. A patient missing all 5 baseline scores will not be eligible for study entry.

General rules for handling missing data:

- Rules for handling missing data for efficacy assessments: No imputation will be required for the MMRM model.
- If the start date of an AE or concomitant medication is incomplete or missing, it will be assumed to have occurred on or after the intake of study medication, except if an incomplete date (eg, month and year) clearly indicates that the event started prior to treatment. If the partial date indicates the same month or year of the intake of study medication date, then the start date by the study medication intake date will be imputed, otherwise, the missing day or month by the first day or the first month will be imputed.
- No imputations will be made for missing laboratory data, ECG data, vital signs data, or physical examination data.

Visit windows:

- Assessments taken outside of protocol allowable windows will be displayed according to the case report form (CRF) assessment recorded by the investigator.

Unscheduled assessments:

- Extra assessments (laboratory data or vital signs associated with non-protocol clinical visits or obtained in the course of investigating or managing AEs) will be included in listings, but not summaries. If more than 1 laboratory value is available for a given visit, the first observation will be used in summaries and all observations will be presented in listings.

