5.8. Analysis of Safety Data

The analysis of safety and tolerability will be performed on the SAF, as defined in [Section 3.3](#). The safety analysis will be based on the reported AEs and other safety information (clinical

laboratory evaluations, vital signs, physical exam and 12-lead ECG). Thresholds for Potential Clinically Significant Values (PCSV) in laboratory variables, vital signs and ECG are defined in [Appendix 10.2](#).

The summary of safety results will be presented for each treatment group.

Period of observation: The observation period will be divided into three segments: pre-treatment, on-treatment, and follow-up period.

- The pre-treatment period is defined as the time from signing the ICF to before the first dose of study drug.
- The on-treatment period is defined as the day from first dose of study drug to 4 weeks after the last dose of SC study drug or 8 weeks after the last dose of IV study drug, whichever is later.
- The Post/Treatment follow-up period is defined as from the end of the on-treatment period+1 day to the end of study visit (week 36).

Unless otherwise noted, summaries of safety variables will use data from the on-treatment period. Listings of safety variables will include data from all periods and values occurring during the pre-treatment and follow-up period will be flagged in the listings.

Day 1 is the first day of investigational product, Day –1 is the day before, and there is no Day 0.

The time interval to detect any on-treatment event or abnormality is the on-treatment period. Data collected outside this interval will be excluded from the estimation of descriptive statistics and identification of abnormalities for laboratory evaluations, ECGs and vital signs. All post-baseline data during the interval will be using in the PCSV analysis including scheduled and unscheduled assessments.

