6.5. Visit Windows

By-visit analysis (including efficacy, laboratory data, vital signs, ECG, ADA) will be summarized by the nominal visit number and no visit window will be defined. Assessments taken outside of protocol allowable windows will be displayed according to the case report form (CRF) assessment recorded by the investigator. For assessments without a nominal visit number such as EOT and EOS assessments, a visit number will be assigned based on the actual visit date using the study day and visit window as in [Appendix 10.2 Table 1](#) Schedule of Events.

The following visit windows will be used to map the unscheduled visits, early end of treatment visits, early study termination visits and daily electronic dairy entries, based on the study day:

Visit No.	Visit	Targeted Study Days*	Analysis Window in Study Days
1	Screening	Day -37 to day -8	≤8
2	Pre-randomization	Day -7 to -4	-7 to -3
3	Baseline	1	1
4	Week 2	15	[12,18]

5	Week 4	29	[22, 36]
6	Week 8	57	[50, 64]
7	Week 12	85	[78, 92]
8	Week 16 (End of Treatment)	113	[106, 120]
9	Week 20	141	[134, 148]
10	Week 36 (End of Study)	253	[246,260]

*Study days are calculated from the first administration of study drug (Day 1)

If multiple measurements occur within the same analysis window, the following rules will be used to determine the analysis value:

- When multiple valid measurements occur within the same analysis window, the closest to the target study day will be used in the analysis.
- When multiple valid measurements occur within equal distance from the target study day, the value after the target study day will be used in the analysis.

Both scheduled and unscheduled measurements will be considered for determining abnormal/PCSV values from laboratory, vital sign or ECG as well as the baseline values.

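### The SAP's baseline pain window includes Day 1, the first-dose day, although baseline is defined as the five days before randomization

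*SAP*

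**What the plan says.** **SAP.** Section 4.4.1 defines baseline as the mean of the non-missing daily LBPI scores "for 5 days prior to randomization (from Day -4 to Day 1"). Section 6.3 repeats the definition. Section 5.8 fixes the day numbering, with Day 1 as the first day of study drug "and there is no Day 0". The note to the Section 6.5 table agrees: "Study days are calculated from the first administration of study drug (Day 1"). That table is to be applied to daily diary entries, among other data, and it assigns Day 1 to Baseline.

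**Protocol.** Section 9.6 states: "Baseline will be defined as the average daily LBPI score for the 5 days before randomization". It adds: "A patient missing all 5 baseline scores will not be eligible for study entry". Section 6.2.4 states: "The date of the first dose of study drug is designated as day 1". Section 3.1 places randomization at the Day 1 visit and ends the pre-randomization period on Day -1.

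**Timing of the score.** Table 1, footnote 8 of the protocol has LBPI recorded "by the patient each day (at approximately 6:00 PM) using the EDiary". SAP 4.4.1 explains the missing week 16 visit-day score by noting that "diaries are available starting at 6pm and clinical visits typically happen during the day". Footnote 6 of the same protocol table makes dosing the last procedure of the visit.

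**The concern.** The label and the day range cannot both hold. Under the range, one of the five values is normally recorded after randomization and after the first dose.

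That value would then sit in three places: the change score, the baseline covariate of the MMRM (SAP 5.7.1), and the denominator of the 30% and 50% LBPI responder definitions (SAP 4.4.3). A covariate that treatment can influence removes part of the treatment effect if treatment acts that early.

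Whatever the bias, two programmers working from Protocol 9.6 and from SAP 4.4.1 would build different primary datasets. SAP 1.1.5, the section reserved for departures from the protocol, lists no change to baseline.

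**Working it through.** **1. Count the days.** With no Day 0, Day -4 to Day 1 is {-4, -3, -2, -1, 1}, which is five days. Without Day 1 it is four. The SAP's figure of five is therefore reproduced only by counting the first-dose day. Five days wholly before Day 1 are Days -5 to -1.

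**2. Place the Day 1 entry in time.** Visits are typically during the day, dosing ends the visit, and the diary opens at 6 PM. The Day 1 diary entry therefore typically follows dosing. No dosing clock time is given, so typically is as strong as this can be put.

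**3. Check against other rules.**
- Protocol 9.6 makes a patient with all five baseline scores missing ineligible. That can be applied only if all five precede randomization.
- SAP 2.1 stratifies on baseline LBPI (<7, ≥7). The stratum must be known before a Day 1 evening score exists.
- SAP 6.1 sets a pre-dose baseline by default, but only where nothing else is specified. Here something else is.

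**4. Weight of Day 1.** With five entries it is 1/5. As pre-dose entries go missing it becomes 1/4, 1/3 or 1/2 for that patient. Exclusion criterion 1 (four or more consecutive missed entries) rules out losing all of Days -4 to -1, so 1/2 is the cap.

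**5. Size of the loss.** Loss in the week 16 difference = slope × Day 1 weight × Day 1 drug–placebo difference. The slopes and Day 1 differences are assumptions; neither document gives them. At weight 1/5:

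| Day 1 difference | slope 0.5 | slope 0.7 | slope 1 (unadjusted change) |
|---|---|---|---|
| 0 | 0 | 0 | 0 |
| 0.2 | 0.020 | 0.028 | 0.040 |
| 0.5 | 0.050 | 0.070 | 0.100 |

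The source results in Protocol 9.2 give 2.18 − 1.25 = 0.93. So 0.070/0.93 = 7.5% and 0.100/0.93 = 10.8%.

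**6. Simulation check.** Week 16 ANCOVA, 2,000 runs, 200 per arm, assumed true effect -0.93, fitted baseline slope 0.63:

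| Day 1 scenario | Days -5 to -1 | Days -4 to 1 |
|---|---|---|
| No effect | -0.934 | -0.934 |
| 0.5-point drop in both arms | -0.929 | -0.929 |
| 0.2-point drop, drug only | -0.928 | -0.902 |
| 0.5-point drop, drug only | -0.932 | -0.869 |

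The last gap, 0.063, equals 0.63 × 0.2 × 0.5, as the formula predicts. A shift common to both arms does no harm.

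**7. Power, for scale only.** SDs from the cited standard errors are 0.14 × √295 = 2.40 and 0.16 × √230 = 2.43, pooled 2.41. At 200 per arm the standard error is 2.41 × √(2/200) = 0.241. Power is Φ(difference/0.241 − 1.96): about 97% for 0.93, 94.5% for 0.86 (loss 0.07) and 93% for 0.83 (loss 0.10).

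**The case against.** The best counter-reading is that the fifth value is a pre-dose score taken at the Day 1 visit. Inclusion criterion 4 requires an LBPI score of at least 4 at the randomization visit, Table 1 marks LBPI on Day 1, and Protocol 6.2.4 puts patient-reported outcomes first and dosing last. Four diary days plus that score would give five pre-dose values. This reading is possible. However, Table 1 footnote 8 and Protocol 6.3.2.1 name site recording only at screening and pre-randomization, and the SAP nowhere says that a visit score would replace the diary entry. The ambiguity is real, and it is itself a reason to amend the text.

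The window may also be deliberate. The pre-randomization visit may fall as late as Day -4, and Day -4 to Day 1 lets even those patients supply five entries. The SAP does not say so, and Protocol 9.6 already allows averaging over fewer scores.

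The conflict with Protocol 9.6 is indirect, because that section gives no day numbers. It needs none: a score taken after the Day 1 visit does not precede randomization.

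The objection on size largely stands. The upper end of the range needs a 0.5-point separation within hours of dosing. The recall period stated for the site-recorded score is 24 hours. If the diary uses the same recall and dosing is at midday (both assumed), about 6 of 24 recalled hours are post-dose, and 0.07 shrinks to 0.07 × 6/24 ≈ 0.02 points, about 2% of 0.93.

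The power figures are weak evidence too, since the planned difference is redacted and 0.93 comes from another drug. None is given for the 563 patients actually randomized: dosing stopped early and the mITT cuts data at 5 weeks after last dose, so the number contributing at week 16 is not known.

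**Conclusion.** The point holds. As written, the SAP's range includes the randomization and first-dose day, contradicts its own label and Protocol 9.6, and will typically bring a post-dose score into the primary baseline.

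The inconsistency is certain from the text. The numerical effect is not: it is zero if the arms agree on Day 1, and otherwise a modest attenuation, up to 0.07 points in the MMRM and 0.10 in unadjusted change under the assumed range. A 24-hour diary recall would make it smaller. Type I error is not inflated. This should be corrected because the primary endpoint needs a single baseline definition, not because the likely bias is large.

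**What to change.** - In SAP 4.4.1 and 6.3, define baseline as the mean of the non-missing daily diary LBPI scores on Days -5 to -1. Alternatively, admit only entries time-stamped before the first dose, and state whether a pre-dose Day 1 visit score counts.
- Add a note to the SAP 6.5 table that post-dose Day 1 diary entries are not mapped to Baseline.
- Record the change before database lock as restoring the Protocol 9.6 definition. Since SAP Section 7 reports two unblinded interim efficacy analyses, also record when the change was made relative to them and that those making it were blinded.
- The Day -4 to Day 1 version may be kept as a sensitivity analysis.

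The cost is two SAP sentences, one table note and one line of code, with no new data. Patients whose pre-randomization visit was on Day -4 contribute four scores instead of five, which Protocol 9.6 already permits.
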